## If clinically indicated only

- 12-lead ECG (single).
- Coagulation: includes prothrombin time or INR and activated PTT (local laboratory).
- Quantitative urinalysis: includes RBC, protein, glucose, pH, ketones, bilirubin, leucocytes, nitrates and specific gravity. To be repeated if hematuria is observed or clinically indicated (local laboratory).
- Qualitative urinalysis (dipstick) (local laboratory).
- Any other examinations that are clinically indicated.

#### 12.4 END OF TREATMENT

The EOT visit will occur 30 ( $\pm$ 7) days after the last IMP administration, or when the patient receives another anti-cancer therapy, whichever is earlier.

The following procedures are to be performed at the EOT visit:

- Physical examination: includes examination of major body systems (neurological, digestive, respiratory [signs and symptoms, respiratory rate] and lymph node examination).
- Body weight.
- Vital signs including blood pressure, heart rate, temperature, and respiration rate.
- Performance status (ECOG).
- All AEs/SAEs, including AEs of new onset as well as worsening of baseline signs and symptoms.
- Concomitant medications.
- New anticancer therapy.
- Blood sample collection for PK and ADA evaluation (central laboratory, see Section 1.5).

## Laboratory assessments

- Serum or urine pregnancy test for WOCBP: a pregnancy test is to be done at the EOT visit (local laboratory).
- Blood chemistry: includes AST, ALT, bilirubin (total and direct), ALP, LDH, sodium, potassium, chloride, bicarbonate/carbon dioxide, calcium, magnesium, phosphate, uric acid, urea or BUN, serum creatinine, eGFR (MDRD formula; Appendix H), glucose (fasting), albumin, total protein, TSH, and free T4 if TSH is outside of the normal range. To be performed every 7 days in cases of Grade 3 or Grade 4 abnormalities (local laboratory).
- Hematology: includes hemoglobin, hematocrit, RBC, WBC with differential, and platelet counts. If Grade 4 neutropenia, assess ANC every 2 to 3 days until ANC  $\geq$ 0.5 × 10^9/L and at least weekly thereafter until ANC  $\geq$ 1.0 × 10^9/L (local laboratory).
- Quantitative or semi-quantitative urinalysis: includes RBC, protein, glucose, pH, ketones, bilirubin, leucocytes, nitrates and specific gravity (local laboratory).

## Exploratory biomarkers (central laboratory, please refer to study flowchart in Section 1)

- Blood sample for tumor genetic markers.
- Blood sample for immunophenotyping.
- Blood sample for plasma or serum cytokines.

## Disease assessment (if not performed in the past 30 days)

- Tumor imaging: CT or MRI scan (the same method of assessment should be used throughout the study).
- Prostate-specific antigen assessment for patients with mCRPC (local laboratory).
- Bone scan for patients with mCRPC. In cases of PD based on bone scan only, the bone scan should be repeated after 6 weeks to confirm the progression. In case of doubtful lesions on bone scan, bone-centered X-ray or MRI scan should be performed to confirm the nature of those lesions (metastatic or not).

## If clinically indicated only

- 12-lead ECG (single).
- Coagulation: includes prothrombin time or INR and activated PTT (local laboratory).
- Qualitative urinalysis (dipstick) (local laboratory).
- Any other examinations that are clinically indicated.

#### 12.5 POST TREATMENT FOLLOW-UP

The post treatment follow-up period includes an extended safety follow-up period of 90 days after the last dose of study treatment and further follow-up beyond 90 days after the last dose of study treatments until death or study cut-off date, whichever occurs first.

## 12.5.1 Safety follow-up period

There will be an extended safety follow-up period for 90 days after the last dose of IMP for ADA assessment and for safety assessment. If REGN2810 or isatuximab ADA testing is positive or inconclusive during post treatment follow-up, ADA testing will be repeated every 3 months until negative.

Patients who discontinue the study treatment without PD will be followed every 90 days for disease assessment until confirmation of PD or start of treatment with another anti-cancer therapy, or until study cut-off date, whichever comes first.

The following procedures are to be performed/assessed at 60 and 90 days after the last IMP administration:

 Physical examination: includes examination of major body systems (neurological, digestive, respiratory [signs and symptoms, respiratory rate] and lymph node examination).

- Vital signs: includes blood pressure, heart rate, temperature, and respiration rate.
- Blood chemistry: includes AST, ALT, bilirubin (total and direct), ALP, LDH, sodium, potassium, chloride, bicarbonate/carbon dioxide, calcium, magnesium, phosphate, uric acid, urea or BUN, serum creatinine, eGFR (MDRD formula; Appendix H), glucose (fasting), albumin, total protein, TSH, and free T4 if TSH is outside of the normal range. To be performed every 7 days in cases of Grade 3 or Grade 4 abnormalities (local laboratory).
- Hematology: includes hemoglobin, hematocrit, RBC, WBC with differential, and platelet counts. If Grade 4 neutropenia, assess ANC every 2 to 3 days until ANC  $\geq$ 0.5 × 10^9/L and at least weekly thereafter until ANC  $\geq$ 1.0 × 10^9/L (local laboratory).
- Quantitative or semi-quantitative urinalysis: includes RBC, protein, glucose, pH, ketones, bilirubin, leucocytes, nitrates and specific gravity (local laboratory).
- Adverse events/SAEs: all ongoing related non-serious AEs, ongoing SAEs at the end of treatment visit (ie, 30 days after last IMP administration), and new related AEs/SAEs are to be followed to resolution or stabilization. Stabilization is defined as an event ongoing without any change for ≥3 months.
- Concomitant medications and relationship to AEs/SAEs.
- New anticancer therapy.
- Serum or urine pregnancy test for WOCBP: a pregnancy test is to be done at every 30 (± 7) days until 6 months after the last dose of study treatment.

## Disease assessment (if discontinue IMP before PD, repeat every 90 days)

- Tumor imaging: CT or MRI scan (the same method of assessment should be used throughout the study).
- Prostate-specific antigen assessment for patients with mCRPC (local laboratory).
- Bone scan for patients with mCRPC. In cases of PD based on bone scan only, the bone scan should be repeated after 6 weeks to confirm the progression. In case of doubtful lesions on bone scan, bone-centered X-ray or MRI scan should be performed to confirm the nature of those lesions (metastatic or not).

## Exploratory biomarkers (central laboratory, please refer to study flowchart in Section 1)

- Blood sample for immunophenotyping (60 days after the last IMP administration only).
- Blood sample for plasma or serum cytokines (60 days after the last IMP administration only).

## 12.5.2 Survival follow-up period

The further follow-up schedule beyond 90 days after last treatment is according to the disease progression status:

• Patients who discontinue study treatment due to progression of disease: phone call follow-up will be done every 90 days from the date of last study treatment administration

until death or study cut-off date. Every effort will be made to follow all patients. If survival follow-up is missed and is not obtained at the time of the scheduled interval, it should be retrieved immediately. For subsequent survival follow-up, the patient follow-up visit should be scheduled at the original scheduled survival follow-up interval. If the patient is unable to visit the clinical center, the follow-up may be done via phone from the Investigator or designee to the patient or the patient's caregiver or a family member, but this should be an exception and any effort should be done to schedule follow-up visit at clinical center.

- Patients who discontinue the study treatment without progression of disease: Will be followed every 90 days for disease assessment until confirmation of progression of disease or start treatment with another anti-cancer therapy. After progression of disease patients will be followed by phone call until death or study cut-off date.
- Patients who are still on study treatment after study cut-off date: will continue to receive study treatment and will undergo planned study procedures (except PK and ADA) until confirmation PD, or start with another anti-cancer therapy, or treatment period ended, whichever comes first.

#### 12.5.3 Post overall survival study cut-off date

Patients still on study treatment after the study cut-off date (12 months after last patient initiates IMP) can continue study treatment until at least 1 treatment discontinuation criterion as defined in Section 6.7 is met. The following information will be collected during the study treatment administration:

- IMP administration.
- Disease assessment (for patients who are still on study treatment, until confirmation of PD, or start with another anti-cancer therapy, or treatment period ended, whichever comes first)
- All SAEs regardless of relationship to study treatment and AEs considered related to study treatment.
- End of treatment reason.

One ADA sample should be drawn 90 days after last study treatment administration. If ADA is positive or inconclusive at 90 days, the repeat samples will be taken every 3 months days until the results become negative (see Section 1.5).

No follow-up information will be collected after these patients discontinue study treatment except all SAEs still ongoing at the end of study treatment and all AEs considered as related to study treatment still ongoing or occurring after the end of study treatment, which will be followed until resolution/stabilization.

11-Jun-2019 Version number: 1

#### 12.6 CROSS-OVER PERIOD

The patients in Cohort A-2 treated with isatuximab monotherapy who experience PD will be permitted to cross over to isatuximab in combination with REGN2810 for up to 2 years after progression on isatuximab monotherapy.

All screening processes for the patients in the Phase 1 and Phase 2 parts are to be conducted before combination IMP initiation for the cross-over part, except informed consent, demography, medical/surgical and disease history, and weight/height. Tumor biopsy at cross-over screening is required unless clinically unfeasible and after discussion with the Sanofi Medical Monitor. On treatment biopsy at Cycle 2, Day 1 (≤7 days; after IMP administration on C1D15 wherever applicable, prior to IMP administration on Cycle 2 Day 1) of the cross-over part is optional (fine needle aspirate is not acceptable). Patients who are included in the cross over part should be evaluated as Cohort A-1 and Cohort B (except PK) in Section 12.3, Section 12.4, and Section 12.5.

Patients who do not meet the cross-over part eligibility criteria should be followed up for safety and survival as detailed in Section 12.5.

## 13 STATISTICAL CONSIDERATIONS

The statistical considerations presented in this section forms the basis for the Statistical Analysis Plan (SAP), which will provide accurate definitions and more detailed specifications for the analyses to be performed on the data collected from this study.

#### 13.1 DETERMINATION OF SAMPLE SIZE

## Phase 1

In Phase 1, approximately 6 (assuming 6 patients for the starting dose) to 24 (assuming 12 patients for the starting dose plus 12 patients for DL-1) DLT evaluable patients are expected to be enrolled. The actual sample size will vary depending on DLTs observed and the number of dose levels explored. Patients who are not evaluable for DLT assessment in the Phase 1 part may be replaced.

#### Phase 2

The Phase 2 part of the study is to evaluate initial anti-tumor activity based on tumor response using RECIST 1.1 criteria for NSCLC and PCWG3 for mCRPC. The efficacy evaluation is based on Simon's 2 stage design with 90% power at 5% 1-sided alpha level for each of the patient cohorts of mCRPC and NSCLC patients, respectively. The assumption of RR, the required sample sizes and the number of responders at each stage are provided in Table 8.

Indication Нο Н₁ Sample size Number (%) of responses to reject Ho Stage 1 **Final** Stage 1 **Final** mCRPC (Combo) 23 49 10% 26%  $\geq 3 (13.0\%)$  $\geq 9 (18.4\%)$ mCRPC (Single) 10% 26% 23 49  $\geq 3 (13.0\%)$  $\geq 9 (18.4\%)$ ≥2 (10.0%) NSCLC (Combo) 5% 22% 20 36  $\geq$ 5 (13.9%)

Table 8 - Sample size calculation

Abbreviations:  $H_0$ =null hypothesis;  $H_1$ =alternative hypothesis; mCRPC=metastatic, castration-resistant prostate cancer; NSCLC=non-small cell lung cancer.

Note: Based on the number of objective responses and the totality of data observed within a treatment cohort in Phase 2 Stage 1, the Sponsor may decide to advance such a treatment cohort to Phase 2 Stage 2 after consulting with Investigators.

Patients who received the recommended dose regimen in Phase 1 will be also included in the Phase 2 Stage 1 (eg, if 6 NSCLC patients were enrolled in Phase 1, only 14 NSCLC patients will be needed to complete the Phase 2 Stage 1 NSCLC cohort).

In Phase 2, approximately 134 patients are expected to be enrolled (assuming Cohort A-1, A-2 and B complete 2 stages), including approximately 66 patients in Phase 2 Stage 1 and approximately 68 patients in Phase 2 Stage 2. The patients who are treated with RP2D in the Phase 1 part will be counted as Phase 2 part patients. If isatuximab 10 mg/kg Q3W in combination

11-Jun-2019 Version number: 1

with REGN2810 or monotherapy without the isatuximab 10 mg/kg QW for 3 weeks is to be tested in a mCRPC or NSCLC cohort, 49 or 36 additional patients will be needed, respectively.

The isatuximab monotherapy cohort (Cohort A-2) will be initiated when the initial anti-tumor activity of isatuximab combination therapy is observed in the Phase 2 Stage 1 according to the study design. When an isatuximab monotherapy cohort (Cohort A-2) is initiated, patients with mCRPC will be randomly assigned in a 1:1 randomization to either the isatuximab in combination with REGN2810 (Cohort A-1) or the isatuximab monotherapy (Cohort A-2). The purpose of the randomization is to avoid the potential bias of patient assignment, and is not to compare between 2 cohorts. Randomization will end when 1 of the 2 cohorts completes the enrollment.

#### 13.2 PATIENT DESCRIPTION

## 13.2.1 Disposition of patients

Screened patients are defined as any patients who signed the study informed consent. The number of screened patients as well as the number and percentage of patients included in the analysis populations defined in Section 13.3 will be provided.

Reasons for treatment discontinuation will be summarized using the all-treated population.

#### 13.2.2 Protocol deviations

Major protocol deviations which compromise the evaluation of the safety and efficacy will be derived adequately and determination of deviations will be finalized based on data review conducted prior to database lock. Decisions made on a patient's status will be documented.

## 13.3 ANALYSIS POPULATIONS

#### 13.3.1 All-treated/safety population

For both Phase 1 and Phase 2 parts of the study, the all-treated/safety population will include all patients who signed the study informed consent and received at least 1 dose (even incomplete) of the study treatments, either isatuximab or REGN2810.

This population is the primary population for the analyses of efficacy and safety parameters except for DLT evaluation. All analyses using this population will be based on the dose level actually received in the first cycle.

## 13.3.2 Patients evaluable for dose-limiting toxicity assessment

The DLT evaluable population is defined as patients in the Phase 1 part receiving the planned doses of isatuximab and REGN2810 during Cycle 1, and who completed the DLT observation period after the first IMP administration as per Section 9.1.1, unless they discontinue the study treatment(s) due to DLT. The dose recommended for Phase 2 will be determined on the DLT evaluable population.

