#### **Analysis populations**

All-treated/safety population: For both Phase 1 and Phase 2 parts of the study, the All-treated/safety population will include all patients who have given their informed consent and received at least 1 dose (even incomplete) of treatments either isatuximab or REGN2810.

This population is the primary population for the analyses of efficacy and safety parameters, unless otherwise noted. All analyses using this population will be based on the dose level actually received in the first cycle.

DLT evaluable population: The DLT evaluable population is defined as patients in the Phase 1 part receiving the planned doses of isatuximab and REGN2810 during Cycle 1, and who completed the DLT observation period after the first IMP administration as per Section 9.1.1, unless they discontinue the study treatment(s) due to DLT. The dose recommended for Phase 2 will be determined on the DLT evaluable population.

ADA evaluable population: The ADA evaluable population will include all patients from the all-treated population with at least 1 non-missing ADA result after the first dose of study treatment.

PK population: The PK population will include all patients from the all-treated population with at least 1 drug concentration after the first dose of study treatment.

Pharmacodynamic population: The pharmacodynamic population will include all patients from the all-treated population with at least 1 pharmacodynamic marker result after the first dose of study treatment.

Cross-over population: The cross-over population is defined as patients in Cohort A-2 who progressed on isatuximab monotherapy and received isatuximab in combination with REGN2810.

Response evaluable population: The response evaluable population will include all patients who fulfill all eligibility criteria in the all-treated population with an evaluable baseline assessment and at least one evaluable post-baseline response assessment during the treatment period.

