### 6.2.1 Starting dose and de-escalation design

The starting dose is selected based on past and ongoing clinical trials. Starting dose is 350 mg Q3W for REGN2810 with isatuximab given 10 mg/kg QW for 3 weeks followed by Q3W. Dose de-escalation will be performed if necessary as defined in Table 1 below:

Table 1 - Dose modification for Phase 1

Dose level	Isatuximab	REGN2810
Starting dose	10 mg/kg QW × 3->Q3W	350 mg Q3W
Minus 1 (DL-1)	5 mg/kg QW × 3->Q3W	350 mg Q3W

Abbreviations: DL=dose level; QW=once weekly; Q3W=once every 3 weeks.

At the starting dose, dose limiting toxicity (DLT) will be assessed in the first 6 patients (1 cycle; 21 days):

• If  $\leq 1/6$  patient has DLT, the starting dose will be the RP2D.

Property of the Sanofi Group - strictly confidential

Page 67

- If 2/6 patients have DLT, 6 additional patients will be enrolled at starting dose level:
  - If a total of 2/12 patients treated at starting dose have DLT, starting dose will be the RP2D.
  - If a total of  $\ge 3/12$  patients have DLT, dose will be de-escalated to dose level minus 1 (DL-1).
- If  $\geq 3/6$  patients have DLT, dose will be de-escalated to DL-1.

An additional 6 patients may be enrolled at DL-1; if  $\leq 1/6$  patient has DLT, DL-1 will be the RP2D. At DL-1, if  $\geq 2/6$  patients have DLT, an alternative dose/schedule might be considered from a safety viewpoint by the Sponsor after consulting with the Investigators who recruit patients for the Phase 1 part. If 2/6 patients have DLT, 6 additional patients will be enrolled at DL-1; if a total of 2/12 patients treated at DL-1 have DLT, DL-1 will be the RP2D. If a total of  $\geq 3/12$  patients have DLT, an alternative dose/schedule might be considered from a safety viewpoint by the Sponsor after consulting with the Investigators who recruit patients for the Phase 1 part.

The DLT observation period is 1 cycle (21 days). The duration of the DLT observation period will be longer for patients who delay initiation of Cycle 2 due to treatment-related AE for which the duration must be assessed in order to determine if the event is a DLT. All AEs during treatment, unless due to disease progression or to a cause obviously unrelated to IMP, will be taken into consideration by the Sponsor and recruiting Investigators for the determination of the maximum tolerated dose (MTD) and RP2D.

IMP initiation of patients in the Phase 1 part is to be staggered by  $\geq 3$  days.

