#### 6.2.2 Maximum tolerated dose

The MTD is defined as the highest dose level at which no more than 1 out of 6 patients (starting dose or DL-1) or 2 out of 12 patients (starting dose) experience an IMP related DLT. The RP2D is defined as the dose selected for the Phase 2 portion. The Sponsor and recruiting investigators will review the overall data observed to decide MTD and RP2D for the isatuximab and REGN2810 combination.

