### 6.5 RETREATMENT OF PATIENTS

The patient must have recovered to NCI CTC AE Grade ≤1 or to his/her baseline status before initiation of the next cycle at the same dose level. In those cases of clear clinical benefit, a patient will continue treatment until disease progression confirmed by imaging 4 weeks after initial evidence of progression (or 6 weeks for bone progression in mCRPC in Appendix A) as detailed in Section 6.7.1, unacceptable AE, patient's decision, 2 years of uninterrupted delivery of IMP without documented PD, or administrative reasons.

A cycle is 21 days, and deemed to have been delayed if the treatment is >3 days beyond the theoretical day of treatment. The reason for dose delay will be provided. In the event of toxicity including DLT, in order for patients to be retreated, see Section 6.6 and Appendix G for retreatment recommendations.

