### 6.6.2 Dose delay and dose omission

Within a cycle, the treatment window is  $\pm 1$  day for each of the weekly administrations and  $\pm 2$  days for each of the Q3W administrations. Within a cycle, a dose is deemed to have been delayed if the treatment is  $\geq 2$  days beyond the theoretical day of treatment for weekly dose, and  $\geq 3$  days beyond the theoretical day of treatment for Q3W dose. The patient will receive the next infusion after recovery of the toxicity as described in Section 6.6.3.

Patients may have dose delay, cycle delay, or dose omission if toxicity occurs and he/she does not recover according to following rules:

- In Cycle 1 (for weekly administration of isatuximab) if toxicity occurs and the patient does not recover on the day of planned infusion or within the following 3 days, infusion of isatuximab (in D8 or D15) may be omitted.
- In Cycle 2 and beyond, if toxicity occurs and the patient does not recover on the day of planned infusion or within the following 14 days, either infusion of isatuximab or REGN2810 may be omitted for combination cohort.
- In case of cycle delay or dose omissions for the recovery of toxicity, the following rules should be followed for restart or discontinue the treatment:
  - In case of a cycle delay up to 14 days or a dose omission, it is per Investigator's decision to restart the study treatment.
  - After a cycle delay of >14 days and ≤84 days, or 2 to 4 consecutive dose omissions, it is per Investigator's decision to restart the study treatment or the IMP that is omitted, if a clear benefit from therapy is observed and after consultation with the Sponsor.
  - The study treatment must be definitely permanently discontinued if the cycle delay is longer than 84 days, or if more than 4 consecutive dose omissions, the IMP will be prematurely discontinued.

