#### 6.6.3 Dose modifications

Guidelines for isatuximab and REGN2810 dose modifications and treatment discontinuation due to hematological and non-hematological adverse reactions in general are outlined in Table 2.

See Section 6.6.4 and Appendix G for guidance for irAEs correlated with REGN2810, and Section 6.6.5 for IARs correlated with isatuximab and REGN2810.

The final decision will be based on the Investigator's judgment, in the best interest of the patient.

11-Jun-2019 Version number: 1

Table 2 - Isatuximab and REGN2810 dose modification guidelines

NCI CTCAE V4.03	management	management	Action and Guidelines
Hematological toxicity			
Grade 1, 2, 3	No change		Patient should be given supportive care and monitored closely.
Grade 3 thrombocytopenia asting >7 days or associated with bleeding	Delay the cycle until bleeding is controlled and platelet >50,000/mm³. Restart treatment with same dose and schedule.		Patient should be given supportive care and monitored closely.
Grade 4	Delay the cycle until ANC >1000/mm³, and platelet >50 000/mm³. Restart with same dose and schedule.  Grade 4 lymphopenia: no change in dose		Permanent discontinuation of study treatment should be considered if toxicity does not resolve within 84 days of last infusion.
Febrile neutropenia and/or neutropenic infection	Delay the cycle until fever and infection recover and ANC >1000/mm³. Restart with same dose and schedule.		
Non-hematological toxicity (other than irAE and IAR)			
Grade 1	No change		N/A
Grade 2 (except alopecia) Grade 3	Delay the cycle until improves to Grade ≤1 or baseline.  Restart treatment at same dose and schedule		It is up to the Investigator's judgment whether to restart the treatment of isatuximab and REGN2810 if the cycle delay is within 14 days.
Grade 4	Permanently discontinue treatment for treatment related AEs		
			If the cycle delay is longer than 14 days, before restarting the treatment, the Investigator must discuss with Sponsor; if it is determined that it is to the best interest of the patient, the treatment may be restarted.  If the cycle delay is longer than 84 days, the treatment must be discontinued.
Immune-related AE: see Table 3 and Appendix G for dose modification and patient management guideline			
Infusion-Associated Reaction: see Table 4 for IAR management guideline			

Abbreviations: AE=adverse event; ANC=absolute neutrophil count; DL-1=dose level minus 1; IAR=infusion-associated reaction; irAE=immune-related adverse event.

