2.3.2 DLT-evaluable population

The DLT evaluable population is defined as patients in the Phase 1 part receiving the planned doses of isatuximab and REGN2810 during Cycle 1, and who completed the DLT observation period after the first IMP administration as per Section 9.1.1 from protocol, unless they discontinue the study treatment(s) due to DLT. The dose recommended for Phase 2 will be determined on the DLT evaluable population.

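### As defined, a Phase 1 patient with a DLT who omits a Day 8 or Day 15 dose but stops neither drug is not DLT-evaluable, so the event can drop out of the count that sets the RP2D

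*Protocol*

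**What the plan says.** Evaluability has two conditions: "receiving the planned doses of isatuximab and REGN2810 during Cycle 1, and who completed the DLT observation period after the first IMP administration" (SAP 2.3.2). Protocol 13.3.2 and the Analysis populations paragraph of the clinical trial summary have the same conditions. All three places give one exception and tie the dose decision to this population: "unless they discontinue the study treatment(s) due to DLT. The dose recommended for Phase 2 will be determined on the DLT evaluable population".

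Other sections bear on who meets that definition:

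- Section 6.6.2 covers weekly dosing in Cycle 1. If toxicity has not resolved on the planned day "or within the following 3 days, infusion of isatuximab (in D8 or D15) may be omitted".
- Section 6.5 contemplates further treatment after a DLT: "In the event of toxicity including DLT, in order for patients to be retreated, see Section 6.6".
- Table 2 in Section 6.6.3 has a Grade 3 non-haematological event delayed and then resumed: "Restart treatment at same dose and schedule". Its Grade 4 haematological row also restarts at the same dose and schedule.
- Section 13.1 lets patients who are not evaluable for DLT be replaced. Section 11.2 says the same and refers to Section 6.2.2 for the method.
- The decision rule in Section 6.2.1 uses a different denominator term: "If a total of 2/12 patients treated at starting dose have DLT, starting dose will be the RP2D".
- Section 6.2.2 adds a judgement step: "The Sponsor and recruiting investigators will review the overall data observed to decide MTD and RP2D".
- Protocol 13.4.5.1 and SAP 2.4.6.1 list DLTs for the DLT-evaluable population only.

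**The concern.** The dosing condition is there so that a patient who was under-treated and had no toxicity does not count as a safe observation. It should not remove a patient whose missed dose was caused by the toxicity being counted. As written it can. The exception rescues a patient who stops one or both drugs because of a DLT, but not one who omits a dose because of a DLT and carries on.

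Exclusion of this kind depends on having had the event, so it cannot be neutral: it can only lower the observed DLT count. With cohorts of six, a single uncounted DLT is enough to change the dose decision. The two texts also disagree on whether this patient counts, since the patient was treated at the dose level (6.2.1) but is not evaluable (13.3.2).

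**Working it through.** **1. Does the text exclude this patient?** Take a Phase 1 patient with a DLT who omits Day 8 or Day 15 isatuximab because of it and later resumes.

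- Planned Cycle 1 doses received? No; one isatuximab dose is missing.
- Exception met? No. SAP 2.4.4.2 calls a dose omitted when it is missed at its scheduled visit and later doses follow. SAP 2.2 and 2.4.6.2 define discontinuation as permanently stopping one drug or stopping all of them. Omission is a separate category.
- Any other route in? No passage sets a minimum fraction of planned doses or says that a DLT alone makes a patient evaluable.

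The patient is therefore not evaluable and may be replaced (13.1). Section 11.2 does not help, because Section 6.2.2 contains no replacement rule.

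**2. Can it occur?** Yes. Two DLT types in 9.1.1 are Grade 3 non-haematological events lasting more than 3 days and Grade 4 neutropenia for at least 7 consecutive days. Table 2 delays and restarts both. A 7-day run beginning on any of Days 2 to 15 includes Day 8 or Day 15.

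**3. The plan's own figure.** The stated 6 to 24 DLT-evaluable patients reproduces: minimum 6; maximum (6 + 6) + (6 + 6) = 24.

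**4. Effect of one uncounted DLT**, if the replacement has none:

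| True result | Rule | Counted result | Rule |
|---|---|---|---|
| 2/6 | add 6 patients | 1/6 | starting dose is RP2D |
| 3/6 | de-escalate | 2/6 | add 6 patients |
| 3/12 | de-escalate | 2/12 | starting dose is RP2D |

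**5. Effect on the chance of accepting the starting dose.** Let p be the true DLT rate and f the share of DLT patients dropped and replaced. The documents give neither, so both are assumptions. Evaluable patients are those with a counted DLT, p(1 − f), plus those without a DLT, 1 − p. The DLT rate among them is

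q = p(1 − f) / (1 − pf).

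From the rule in 6.2.1,

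P(accept) = P(X ≤ 1 | 6, q) + P(X = 2 | 6, q) × P(X = 0 | 6, q).

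- p = 0.33, f = 0: q = 0.330; 0.0905 + 0.2673 + 0.3292 × 0.0905 = 0.388.
- p = 0.33, f = 0.25: q = 0.2475 / 0.9175 = 0.270; 0.1516 + 0.3361 + 0.3104 × 0.1516 = 0.535.

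| True DLT rate p | f = 0 | f = 0.10 | f = 0.25 | f = 0.50 |
|---|---|---|---|---|
| 0.20 | 0.720 | 0.762 | 0.825 | 0.920 |
| 0.25 | 0.587 | 0.638 | 0.720 | 0.859 |
| 0.33 | 0.388 | 0.441 | 0.535 | 0.726 |
| 0.40 | 0.248 | 0.293 | 0.380 | 0.587 |

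The f = 0 column is the behaviour once every DLT patient counts. The model assumes independent patients, replacements subject to the same rule, and no override of the count by the review group.

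**The case against.** The case for treating this as minor has four parts.

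**The affected set is small.** Many DLTs stop a drug and so meet the exception: related Grade 4 non-haematological events (Table 2), and Grade 3-4 pneumonitis, Grade 3-4 renal failure and Grade 3 or higher uveitis, for which Appendix G discontinues REGN2810. Others leave isatuximab unchanged (Grade 2 uveitis, Grade 3 skin events), miss no Cycle 1 dose (Cycle 2 delay), or start after the Day 15 infusion. Omission and replacement are both optional. All of this stands. It makes large values of f unlikely but does not bring f to zero.

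**There are safeguards.** Section 6.2.1 has all on-treatment AEs considered in setting the MTD and RP2D, unless due to progression or obviously unrelated. DLT status is notified before the next cycle (9.1.1), and data are reviewed about every two weeks in Phase 1 (6.9). DLTs are AESIs, and SAP 2.4.6.2 lists every patient with one. The event would very probably be seen. None of these provisions returns it to the x/6 or x/12 count; that would depend on a judgement the written rule does not require.

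**Discontinue might include a temporary stop.** The title of Protocol Section 11 mentions temporary discontinuation, but its text deals only with permanent discontinuation, and the SAP definitions point the same way.

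**Counting every DLT whatever doses were received could charge an overdose-related event to the dose level.** That is a remote case, and the error would be on the cautious side.

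**Conclusion.** The concern holds. The definition, identical in substance in three places, leaves out a patient with a DLT who omits a Cycle 1 dose and continues both drugs. It also conflicts with the patients-treated wording of the decision rule. The gap is narrow, but it bears on the population that determines the RP2D and errs in one direction only.

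Its size rests on an unknown share. At a true DLT rate of 33%, the chance of accepting the starting dose moves from 0.39 to 0.44 if 10% of DLT patients are dropped and replaced. The 25% and 50% figures (0.53 and 0.73) are illustrations of the upper range, not expectations. The wording finding does not depend on any of these values. It should be fixed, though it does not undermine the Phase 1 design.

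**What to change.** In Protocol 13.3.2, the clinical trial summary and SAP 2.3.2, state that:

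1. every Phase 1 patient with a confirmed DLT in the observation period is DLT-evaluable, whatever doses were received and whether or not treatment continues;
2. the planned-dose and completed-observation conditions apply only to patients without a DLT;
3. only patients without a DLT may be replaced.

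Use the term DLT-evaluable patients, so defined, as the denominator of the x/6 and x/12 rules in Section 6.2.1 and the summary. Correct the cross-reference in Section 11.2 so that it leads to a stated replacement rule.

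Section 1.5.1 already refers to Phase 2 Stage 1 enrolment, so the Phase 1 decision may have been taken. If so, correct the SAP definition and confirm in the study report that no patient with a DLT was excluded or replaced on these grounds.

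The cost is a few sentences in three places, aligned wording in the decision rule and one cross-reference. No data, patients or treatment rules change.
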